### **15.1.1 Incidence, incidence rates and number of events**

The incidence of an adverse event is defined as the number of subjects with occurrence of this adverse event during the period of interest.

The incidence rate (CIR for crude incidence rate) of an adverse event is defined as the number of subjects with occurrence of this adverse event during the period of interest divided by the total number of subjects  $n$  in the respective group (e.g., treatment group).

The incidence, incidence rate, the number of events and the percentage of events (related to the total number of events) will be summarized by PT sorted by decreasing incidence rate for:

- TEAEs.
- Serious TEAEs.
- Non-serious TEAEs.
- Related TEAEs.

A separate table per type of TEAE will be prepared. The tables will be restricted to events with an incidence rate of at least 5% ( $\geq 5\%$ ).

The incidence, incidence rate, the number of events and the percentage of events (related to the total number of events) will be summarized by SOC and PT (sorted alphabetically) for each:

- TEAEs.
- Serious TEAEs.
- Non-serious TEAEs.
- Related TEAEs.

For serious TEAEs, the incidence, the incidence rate, the number of events and the percentage of events will also be presented for serious related TEAEs, serious fatal TEAEs and serious fatal related TEAEs.

For all enrolled subjects, the incidence, incidence rate, the number of events and the percentage of events (related to the total number of events) will be summarized by SOC and PT (sorted alphabetically) for each:

- Pre-treatment non-TEAEs.
- Serious pre-treatment non-TEAEs.

Presentation will only be overall and not per treatment.

The number and percentage of events will be summarized by SOC and PT (sorted alphabetically) for the following TEAE descriptors. Presentation will be for TEAEs only.

- Intensity: mild, moderate, severe.
- Causal relationship to the IMP: related (with subcategories: possible, probable/likely, certain), not related (with subcategories: not related, unlikely), unknown (with subcategories: conditional/unclassified, unassessable/unclassifiable, causal relationship missing).
- Outcome: recovered/resolved, recovering/resolving, not recovered/not resolved, recovered/resolved with sequelae, fatal, unknown.
- Non IMP related countermeasures: none, newly started medication, trial discontinuation, others.
- Action taken with IMP: drug interrupted, drug withdrawn, not applicable, unknown.

Denominator for percentage calculation will be the number of all TEAEs for presentation overall SOCs, and the number of TEAEs per SOC or PT respectively, for the presentation per SOC or PT, respectively.

Measures of location and variation will be calculated for:

- Duration of TEAEs.
- Time to onset of TEAE.

In addition, the time to onset of TEAE will be summarized using time-to-event methods pooled over all TEAEs. Time will be days until onset. The time to onset will be censored at the End-of-Trial-Visit, or at the time point of discontinuation if not due to TEAE.

The following listings will be produced for all enrolled subjects:

- Deaths.
- Serious adverse events other than death.

- Adverse events leading to discontinuation from the trial.
- Adverse events leading to permanent discontinuation from IMP.

In addition, adverse events associated with acute phase reaction will be presented for the SAF in a separate subject data listing. Adverse events associated with acute phase reaction include the PTs *Acute Phase Reaction* in all cases. They also include the PTs *Arthralgia*, *Bone pain*, *Chills*, *Fatigue*, *Headache*, *Influenza Like Illness*, *Musculoskeletal Chest Pain*, *Musculoskeletal Pain*, *Myalgia*, *Pain*, *Pain In Extremity* and *Pyrexia*, but only if occurring in the first 3 days after first IMP intake and not lasting longer than 3 days.

For TEAEs associated with the acute phase reaction, the incidence, incidence rate, the number of events and the percentage of events (related to the total number of events) will be summarized by PT.

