### **14.1.6 Analysis of safety data**

#### **14.1.6.1 Adverse events**

A definition of adverse event is given in Section [12.3.1](#).

The original terms recorded in the CRF to identify adverse events will be coded using the most recent version of the Medical Dictionary for Regulatory Activities (MedDRA) at the time of database lock.

All adverse events occurring in a subject administered a trial treatment and which do not necessarily have a causal relationship with this treatment will be defined as TEAEs. In addition, pre-treatment adverse events which worsen during the treatment period are also considered TEAEs.

Treatment emergent adverse events will be summarized for each treatment group by System Organ Class and Preferred Term. Additional summaries by time to onset, duration, intensity, relationship to the IMP, outcome, expectedness, and countermeasures will also be created. To account for the differences in the planned trial duration of the subjects in this trial, an analysis of exposure-adjusted incidence rates will be done in addition to the analysis of crude incidence rates.

Subjects with SAEs will be summarized and additionally listed. Special attention will be given to those subjects who discontinue treatment due to an adverse event or who experience a severe or SAE.

The incidences and incidence rates of all adverse events will be summarized descriptively.

Permanent discontinuations from treatment due to adverse events will be summarized descriptively.

The distribution of time to onset of any TEAE will be summarized using time-to-event methods. A graphical display using Kaplan-Meier methods displaying subjects at risk per time point will also be produced.

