### 15.1 Adverse events

All adverse events with start date/time after first IMP administration in a subject administered a trial treatment will be defined as treatment emergent adverse events (TEAE) irrespective of causal relationship.

A pre-treatment non-TEAEs is an adverse event starting in the pre-treatment period as defined in Section 8.2.2.

If there are partial dates or times, an adverse event will be considered treatment emergent unless the information available will clearly exclude it. Further details can be found in Section 20.1.6.1.

The causal relationship of TEAEs to IMP is categorized as follows:

Category	Assessment by investigator:
Related	certain probable/likely possible
Not related	unlikely not related
Unknown	unassessable/unclassifiable conditional/unclassified causal relationship is missing

A TEAE is considered to be ‘expected’ when the nature or intensity is consistent with the information in the neridronic acid investigator’s brochure. Otherwise, it is considered to be an ‘unexpected’ TEAE. Expectedness will be assessed by the sponsor.

The following overview tables will be generated overall, i.e., for the single treatment group neridronic acid 400 mg.

1. Summary of the number and percentage of subjects with at least 1:

- TEAE.
- Serious TEAE.
- Non-serious TEAE.
- Unexpected TEAE.
- Related TEAE.
- Related serious TEAEs.
- TEAE leading to discontinuation from IMP.
- TEAE leading to discontinuation from the trial.
- Deaths.

The percentage denominator will be the number of subjects.

2. Summary presenting the number of TEAEs per subject categorized as 0, 1, 2, 3, 4, 5, and >5.
3. Summary of the number and percentage of TEAEs for:
  - TEAEs.
  - Serious TEAEs.
  - Non-serious TEAEs.
  - Unexpected TEAE.
  - Related TEAEs.
  - Related serious TEAEs.
  - TEAE leading to discontinuation from IMP.
  - TEAE leading to discontinuation from the trial.

The percentage denominator will be the total number of TEAEs.

If more than 10 subjects discontinue the trial/IMP due to TEAE, the incidence and the incidence rate of TEAEs leading to discontinuation from the trial/from IMP will be summarized by SOC and PT.

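### No planned summary counts subjects with a severe TEAE: SAP 15.1.1 tabulates intensity by event only, and severe TEAEs have no dedicated listing

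*SAP*

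**What the plan says.** **Protocol 14.1.6.1** sets out two relevant intentions. One is a set of descriptive summaries that includes intensity: "Additional summaries by time to onset, duration, intensity, relationship to the IMP, outcome, expectedness, and countermeasures will also be created". It does not say whether the unit is the subject or the event. The other singles out certain people: "Special attention will be given to those subjects who discontinue treatment due to an adverse event or who experience a severe or SAE".

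**SAP 15.1** plans a subject-level overview, introduced as "Summary of the number and percentage of subjects with at least 1". Its nine items are any, serious, non-serious, unexpected, related and related serious TEAEs, TEAEs leading to discontinuation of the investigational product, TEAEs leading to discontinuation from the trial, and deaths. Severe TEAE is not among them.

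**SAP 15.1.1** plans incidence tables with subject counts by System Organ Class (SOC) and Preferred Term (PT): "The incidence, incidence rate, the number of events and the percentage of events (related to the total number of events) will be summarized by SOC". They cover all, serious, non-serious and related TEAEs. TEAEs associated with the acute phase reaction are summarized separately by PT.

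Intensity appears among the descriptors in the same section ("Intensity: mild, moderate, severe"), under the rule "The number and percentage of events will be summarized by SOC and PT (sorted alphabetically) for the following TEAE descriptors". The denominator is also events: "Denominator for percentage calculation will be the number of all TEAEs for presentation overall SOCs", and the TEAEs within the SOC or PT at the lower levels.

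The dedicated listings begin "The following listings will be produced for all enrolled subjects". They cover deaths, other serious events, events leading to trial discontinuation and events leading to permanent discontinuation of the product. A separate listing covers acute phase reaction events.

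**The concern.** Safety and tolerability is the primary objective, and the primary endpoint is whether a subject had any TEAE. That endpoint does not grade severity. How many people had a severe event is a basic tolerability result, and with intensity tabulated by event no planned table gives it. An event-level table cannot separate a few subjects with many severe events from many subjects with one each. Those two pictures call for different descriptions of how well the drug is tolerated.

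The protocol puts subjects with a severe event alongside two other groups. The SAP gives those two groups a subject count and a listing, and gives the severe group neither.

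**Working it through.** The plan states no figure on this point, so there is nothing to reproduce. The check sets the three groups named in Protocol 14.1.6.1 against the planned outputs.

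| Group named in the protocol | Subject count in SAP 15.1 overview | Dedicated listing in SAP 15.1.1 |
|---|---|---|
| Treatment discontinued because of an adverse event | Yes | Yes |
| SAE | Yes | Yes (deaths, and other serious events) |
| Severe adverse event | No | No |

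**Could another output supply the count?**

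- The SAP 15.1 summary of TEAEs per subject (0 to more than 5) is not split by intensity.
- The serious rows do not stand in for severe. Protocol 12.3.1 defines severe by the effect of symptoms on daily activity, and defines serious by a separate set of criteria such as death, danger to life or hospital admission. A severe event that is not serious falls outside every serious row and listing.
- The discontinuation row does not stand in either. Under Protocol 9.3.2, discontinuation of the product concerns the treatment period only, which is four infusions over 10 days. SAP 8.2.2 runs the on-treatment period to Visit 11 (Week 52). A severe event after the last infusion cannot lead to stopping the product.
- SAP 20.1.6.1 derives no worst intensity per subject, and SAP 7.1 records no change from the protocol on this point.

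**Illustration.** The only input from the documents is N = 290 (Protocol 1.5.1 and SAP 5.2). Every event count below is assumed. Take 30 severe TEAEs.

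What the planned table would show is severe events / all TEAEs:

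- 600 TEAEs: 30/600 = 5.0%
- 1000 TEAEs: 30/1000 = 3.0%
- 1500 TEAEs: 30/1500 = 2.0%

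What it would not show is subjects with at least one severe TEAE / 290 (exact Clopper-Pearson 95% intervals):

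| Subjects with the 30 severe events | Percentage of 290 | 95% interval |
|---|---|---|
| 6 (5 events each) | 2.1% | 0.8% to 4.4% |
| 15 (2 events each) | 5.2% | 2.9% to 8.4% |
| 30 (1 event each) | 10.3% | 7.1% to 14.4% |

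For any fixed total of TEAEs, the overall row of the intensity table is the same in all three cases. The subject percentage differs by a factor of 30/6 = 5.

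**The case against.** The case against has four parts, and much of it stands.

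1. **The table gives counts as well as percentages.** A reader might infer from the denominator rule that severe events are shown only as a diluted percentage. They are not, because the number of severe events is shown by SOC and PT. That number is also an upper limit on the number of subjects affected. If each affected subject had exactly one severe event, the event count would equal the subject count and nothing would be hidden. The loss arises only when subjects have more than one.

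2. **Severe events are listed somewhere.** A reader might infer that no output shows them, or that the subject count cannot be obtained at all. SAP 8.1 and Protocol 14.1.2 provide for listing all collected and derived data, and intensity is recorded for every adverse event. Severe events that are serious, led to discontinuation or belong to the acute phase reaction also appear in a dedicated listing. The count could therefore be made by hand.

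3. **The protocol promises no specific output.** A reader might infer that the SAP contradicts the protocol. Special attention is not defined as a table or a listing. The sentence before it does promise a summary and a listing, but for subjects with SAEs only. The intensity summary is promised without a counting unit, and the SAP supplies one.

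4. **No endpoint changes.** The primary endpoint and the secondary safety endpoint are both subject-level and are unaffected, and worst intensity per subject can be derived later.

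The gap in the planned summaries remains. A hand count from a general listing is not a pre-specified result, and this trial is meant to support product registration.

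**Conclusion.** The point holds in a limited form. Intensity is summarized at event level only, no planned summary gives the number or percentage of subjects with at least one severe TEAE, and there is no dedicated listing of severe TEAEs. Of the three groups that the protocol names together, this is the only one without both outputs.

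It is a protocol intention that the SAP has not turned into an output. The documents do not support calling it a contradiction, and they do not show that information is lost.

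The size depends on how severe events cluster within subjects, which the documents do not say. With the assumed 30 events in 6 to 30 subjects, the range is 2.1% to 10.3% of 290. If severe events rarely recur in the same subject, the practical effect is small. The change is a desirable improvement, and the trial's conclusions do not depend on it.

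**What to change.** Make three additions to the SAP:

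1. In the subject-level overview of SAP 15.1, add a row for subjects with at least one severe TEAE.
2. In SAP 15.1.1, add a table of subjects by maximum intensity, by SOC and PT, with the number of subjects in the Safety Set as the denominator. State the derivation in SAP 20.1.6.1: each subject counts once per SOC and once per PT, at the worst intensity recorded. Keep the event-level table beside it.
3. Add a listing of severe TEAEs to the dedicated listings in SAP 15.1.1.

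The cost is one row, one table and one listing. No new data are needed, because Protocol 12.3.1 already has the maximum intensity of each event recorded. The SAP also already takes a worst value per subject for categorical laboratory, vital-sign and ECG parameters (SAP 15.2), so the approach is familiar within the plan.

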### **Potential risks and risk management of neridronic acid**

#### *Acute phase reaction*

The most common side effects associated with parenteral administration of aminobisphosphonates are flu-like symptoms, commonly referred to as "acute phase reaction" (Reid et al. 2010; Silverman et al. 2011). Symptoms include fever, myalgia, fatigue, headache, diarrhea, arthralgia, muscle pain, and bone pain. These are self-limiting and usually resolve after 24 hours to 48 hours. Symptoms of the acute phase reaction typically occur following the first administration and are absent or decreased following subsequent administrations. For symptomatic management of the acute phase reaction, oral acetaminophen (paracetamol), is recommended, starting from approximately 1 hour prior to the first infusion and then approximately every 6 hours for the 72-hour period after the first infusion. Commercially available products and dosages can be used as available in the country where the trial is performed. However, the total dose of acetaminophen, including any other medications that contain acetaminophen, must not exceed 4 g/day, due to acetaminophen's known risks for hepatic toxicity. Non-steroidal anti-inflammatory drugs should not be used to alleviate the symptoms of the acute phase reaction due to their potential to cause acute changes in renal function, which may confound renal safety assessments.

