#### **Handling of missing date information**

The term missing date/time refers to a completely missing date/time or to an incomplete date/time where parts are not available, e.g., missing hours.

If the number of adverse events with missing date information does not exceed 10% the following imputation strategy is applied.

Missing start and end date/times will be imputed conservatively, i.e., missing values will be imputed in such a way that the duration of the adverse event is considered with the longest possible duration and such that, whenever the adverse event may potentially start after first IMP administration, the adverse event will be handled as a TEAE.

I1-I4: imputation steps

C1-C4: checkpoints

Figure 2: Graphical overview about the imputation strategy

Further explanations on the flow chart:

The different steps of the displayed imputation strategy must be completed from the first to the last step. All procedures in each step must be completed in the order given.

- Imputation:

- I1: Impute with date/time of first IMP
- I2:
  - a) Impute with first calendar day and/or first calendar month.  
Imputation will be done based on the available partial information starting with month and then day. The respective first month and day will be chosen for imputation:

Missing date	Imputed date
2014-Mar	2014-Mar-01
2014	2014-Jan-01

- I2:
  - b) Impute with first hour and/or first minute.  
Imputation will be done based on the available partial information starting with hour and then minutes. The respective first hour of a day and first minute will be chosen for imputation. “00:00” will be considered as the first hour/ first minute per day.

Missing time	Imputed time
11:--	11:00
--:--	00:00

- I3: Impute with date/time of informed consent signed  
If signing of informed consent was not collected with time information set adverse event start time to 00:00.
- I4:
  - a) impute with last calendar day and/or calendar last month  
Imputation will be done based on the available partial information starting with month and then day. The respective last month and day will be chosen for imputation:

Missing date	Imputed data
2014-Mar	2014-Mar-31
2014	2014-Dec-31

For February, leap years must be taken into account when calculating the last day in February.

1.1. b: impute with last hour and/or last minute

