Imputation will be done based on the available partial information starting with hour and then minutes. The respective last hour of a day and last minute will be chosen for imputation. “23:59” will be considered as the last hour/ last minute per day.

Missing time	Imputed time
11:--	11:59
--:--	23:59

- Checkpoints
  - C1: The decision must be taken based on the available information (date/time) before imputation.
  - C2: adverse event stop date before first IMP
- 1.2. 1) The decision must be taken based on the available information (date/time) before imputation.
  - 2) If the end date is completely missing (with or without the information that the adverse event was continuing), this will be considered as after first IMP.
  - 3) If no IMP was given, this will be treated as adverse event stop date before first IMP.
- C3: The decision must to be taken based on the available information (date/time) before imputation.
- C4: The decision must to be taken based on the available information (date/time) before imputation.

A replacement of missing year for adverse event start information is not foreseen. If needed, this will be considered on a case-by-case decision which must be documented together with the documentation of ADaM data sets.

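### The acute phase reaction summary omits symptom-coded events lasting over 3 days, and imputing end dates to the longest duration removes short events as well

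*SAP*

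**What the plan says.** SAP Section 15.1.1 defines a group of adverse events associated with the acute phase reaction. One term is unconditional: "Adverse events associated with acute phase reaction include the PTs *Acute Phase Reaction* in all cases". Twelve symptom terms follow (arthralgia, bone pain, chills, fatigue, headache, influenza like illness, musculoskeletal chest pain, musculoskeletal pain, myalgia, pain, pain in extremity, pyrexia). These count "but only if occurring in the first 3 days after first IMP intake and not lasting longer than 3 days". The group feeds a separate listing for the Safety Set and a table by preferred term: "For TEAEs associated with the acute phase reaction, the incidence, incidence rate, the number of events and the percentage of events".

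SAP Section 20.1.6.1 governs dates:

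- The condition is: "If the number of adverse events with missing date information does not exceed 10% the following imputation strategy is applied".
- Missing dates are filled so that "the duration of the adverse event is considered with the longest possible duration".
- For a partial end date the step is to "impute with last calendar day and/or calendar last month".
- For a partial end time: "The respective last hour of a day and last minute will be chosen for imputation".
- The paragraph on duration of adverse events calculates duration from the imputed start and stop values. Where it cannot be calculated, duration becomes a category, either continuing or missing.

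Protocol Section 8.2 names flu-like symptoms as the most common side effects of parenteral aminobisphosphonates. It says that they usually resolve within 24 to 48 hours and sets no maximum. Its list reads: "Symptoms include fever, myalgia, fatigue, headache, diarrhea, arthralgia, muscle pain, and bone pain".

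**The concern.** For the 12 symptom terms, membership of the group depends on how the event turns out. Pyrexia that starts on Day 1 and lasts 4 days is left out. A 5-day reaction recorded under the term Acute Phase Reaction is counted, while the same illness recorded as fever and myalgia is not.

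The imputation rule adds to this. Assuming the longest duration is cautious when a long event is the bad outcome. Here a long duration is the ground for exclusion, so the rule takes events out.

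This is a safety trial meant to support registration, and the table concerns the most common reaction that the protocol names. No other planned output isolates these events by onset. The general tables pool a headache on Day 1 with one months later, because the on-treatment period runs to Visit 11. The second infusion is targeted for Day 4, so a Day 1 symptom lasting over 3 days persists to about the time of the next dose. A reader would want to see those cases in this table.

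**Working it through.** The plan gives no expected rate of acute phase reaction, so there is no figure to reproduce. Two checks are possible.

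**1. What the end-date rules do to events truly lasting 3 days or less.** Inputs: the 3-day limit (Section 15.1.1) and the end-date rules (Section 20.1.6.1). Assumptions: 3 days means 72 hours, and start times are spread evenly over the year. Let d be the true duration in days.

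- *End day missing.* The end becomes the last minute of the month. The event stays in only if it starts in the last 3 days of a month and ends in that month. That is a window of 3 − d days in an average month of 365/12 = 30.4 days. Share excluded = 1 − (3 − d)/30.4.
- *End month missing.* By the same argument, share excluded = 1 − (3 − d)/365.
- *Only end time missing.* The end becomes 23:59 of the end date. For d up to 2, the imputed duration cannot exceed 3 days. For d between 2 and 3, it does so when the end falls on the third calendar day after the start date, which has probability d − 2.

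Averages over d, with a simulation of 40,000 events per case as a check:

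| Missing part | d from 0 to 2 | d from 2 to 3 | d from 0 to 3 | Simulation, 0 to 3 |
|---|---|---|---|---|
| End day | 1 − 2/30.4 = 93.4% | 1 − 0.5/30.4 = 98.4% | 1 − 1.5/30.4 = 95.1% | 95.2% |
| End month | 1 − 2/365 = 99.5% | 1 − 0.5/365 = 99.9% | 1 − 1.5/365 = 99.6% | 99.6% |
| End time only | 0% | 50% | 0.5/3 = 17% | 17% |

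Example: a fever starts on 10 April at 18:00 and its end is recorded only as April. The imputed end is 30 April at 23:59, the duration is 20.2 days, and the event is excluded.

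**2. Illustrative size.** N = 290 is the planned number. The true rate p and the share q of affected subjects whose only qualifying symptoms last over 3 days are both assumed. Rate shown = p × (1 − q).

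| p | q = 5% | q = 10% | q = 20% | q = 30% |
|---|---|---|---|---|
| 20% (58 subjects) | 19% (55) | 18% (52) | 16% (46) | 14% (41) |
| 40% (116) | 38% (110) | 36% (104) | 32% (93) | 28% (81) |
| 60% (174) | 57% (165) | 54% (157) | 48% (139) | 42% (122) |

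For the imputation alone, let m be the share of affected subjects whose qualifying event lacks the end day. With p = 40%:

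- m = 10%: 40% × (1 − 0.10 × 0.952) = 36.2%, or 105 subjects.
- m = 1%: 40% × (1 − 0.01 × 0.952) = 39.6%.

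The imputation effect is small unless partial dates are common. The duration limit is the systematic part.

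**Term list.** Each symptom in the protocol's list has a counterpart among the SAP's 12 terms except diarrhea.

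**The case against.** The limit has a rationale. Three days lies beyond the usual course of 24 to 48 hours. Every subject has chronic limb pain of at least 4 on the NRS at baseline, deterioration of the treated disease is itself an adverse event, and several of the 12 terms are pain terms. A duration limit keeps some CRPS pain out. This stands, and it is why the current definition should remain as one row.

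Nothing is lost from the report as a whole. Excluded events still appear in the tables of all, related and serious events, in the intensity and outcome tables, in the overall duration summary, and in the primary endpoint. This also stands, and it limits the point to one listing and one table.

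Partial end dates should be uncommon. Start and end date and time are collected, and the early visits are close together. Imputation applies only up to the 10% threshold, and the flow chart that governs it is not in the text available here, so the check uses the written steps. All of this makes the imputation secondary, but its direction does not change.

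Three stronger readings are tempting and are not supported:

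- *All prolonged reactions disappear.* They do not, because those coded to Acute Phase Reaction stay in.
- *The worst cases are removed.* Only the longest symptom-coded cases are. Protocol Section 12.3.1 grades intensity by tolerability and effect on daily life, so a severe 2-day fever is counted.
- *Continuing events are imputed out.* The SAP gives them a category and no rule for the 3-day test. An event truly continuing at the last visit exceeds 3 days by definition.

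**Conclusion.** The concern holds for the acute phase reaction listing and incidence table. Compared with a definition by term and onset window, the duration limit and the end-date imputation can each only remove events, so the understatement runs in one direction. The table cannot show prolonged reactions recorded as symptoms, and inclusion of a prolonged reaction depends on the wording used.

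The 93% to over 99% exclusion of short events with a missing end day or month follows from the SAP's written rules, given 3 days read as 72 hours and start times spread over the year. The effect on incidence cannot be derived from the documents. A reader might take a loss of 10% to 30% from the second table in the working, but those shares are inputs chosen for illustration. That table also treats every longer event in the onset window as a true reaction, which will not hold for all pain terms. The general adverse event tables and the primary endpoint are unaffected.

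**What to change.** In SAP Section 15.1.1, before the data are locked:

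1. Keep the current definition as one row.
2. Add a row defined by preferred term and onset in the first 3 days after first IMP only. Tabulate duration within it as up to 3 days, over 3 days, or continuing/unknown.
3. Do not let an imputed end date decide inclusion in the duration-limited row. One workable rule is to exclude an event only when the recorded date parts show that it lasted over 3 days. This matches Section 15.1, which treats an event with partial dates as treatment emergent unless the recorded information clearly rules that out.
4. State how continuing and missing durations are classified, and whether 3 days means 72 hours or calendar days.
5. Add diarrhea to the term list, to match Protocol Section 8.2.

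No new data are needed. The cost is one more row in a planned table. That row will include some unrelated pain events of longer duration, which the duration split makes visible.

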#### *Ocular effects*

Eye disorders have been reported with neridronic acid and appear to be associated with the acute phase reaction. These events include anterior uveitis, episcleritis, conjunctivitis and ocular pain. As severe ocular inflammation may increase the potential risk of long-term vision loss, treatment with

neridronic acid will be discontinued at first signs of ocular inflammation, followed by an ophthalmologic exam.

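### The acute phase reaction table in SAP 15.1.1 leaves out diarrhea, which the protocol names as a symptom, and gives no proportion of subjects with at least one such event

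*SAP*

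**What the plan says.** Protocol 8.2, under its heading on the acute phase reaction, states: "The most common side effects associated with parenteral administration of aminobisphosphonates are flu-like symptoms, commonly referred to as" the acute phase reaction. It then lists the symptoms: "Symptoms include fever, myalgia, fatigue, headache, diarrhea, arthralgia, muscle pain, and bone pain". On timing it says that they "typically occur following the first administration and are absent or decreased following subsequent administrations".

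SAP 15.1.1 gives the reaction its own definition, listing and table. The PT Acute Phase Reaction counts in every case. Twelve symptom PTs also count (Arthralgia, Bone pain, Chills, Fatigue, Headache, Influenza Like Illness, Musculoskeletal Chest Pain, Musculoskeletal Pain, Myalgia, Pain, Pain In Extremity, Pyrexia), "but only if occurring in the first 3 days after first IMP intake" and only if their duration is at most 3 days. The table is specified as follows: "For TEAEs associated with the acute phase reaction, the incidence, incidence rate, the number of events and the percentage of events", summarized by PT. The same section defines incidence as a count of subjects with the event. No row for subjects with any event from the list is specified.

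**The concern.** The SAP sets out to characterize this reaction separately, so its definition should match the protocol's description, and the table should answer the first question a reader will ask: what share of subjects had the reaction? As written it falls short on both counts.

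Diarrhea is missing from a closed list and no reason is given. Lack of specificity cannot be the reason, because Headache, Fatigue and Pain are on the list.

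A table by PT gives one overlapping rate per symptom and no total. The trial is meant to supply safety data for registration (Protocol 6.4 and 8.1), and its primary endpoint is any treatment emergent adverse event (TEAE). Without a composite row, a reader cannot see how much of that endpoint comes from the best-known reaction to this drug class. The composite would then have to be built after the data are seen.

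**Working it through.** The documents state no rate for the reaction, so there is no figure to reproduce. The check has three steps.

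**1. Term list.** The symptoms in Protocol 8.2 are set against the PTs in SAP 15.1.1.

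| Protocol 8.2 symptom | PT in SAP 15.1.1 |
|---|---|
| fever | Pyrexia |
| myalgia | Myalgia |
| fatigue | Fatigue |
| headache | Headache |
| diarrhea | none |
| arthralgia | Arthralgia |
| muscle pain | Myalgia |
| bone pain | Bone pain |

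Seven of eight have a match. Adding diarrhea would change a composite count only for subjects whose sole qualifying event is diarrhea, since anyone with another listed symptom in the window is already in. The documents give no rate from which to size that group.

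**2. Is the composite specified elsewhere?** The overview in SAP 15.1 counts subjects with at least one event in nine categories (any TEAE, serious, non-serious, unexpected, related, related serious, leading to discontinuation from IMP, leading to discontinuation from the trial, deaths). None is the acute phase reaction. The other tables in SAP 15.1.1 are by PT, or by System Organ Class (SOC) and PT. SAP 15.5 covers any TEAE only. No specified table gives the composite.

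**3. Can it be derived from the PT rows?** Let r1, r2, … be the PT incidence rates. Because each counts subjects and one subject can appear in several rows,

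max(r1, r2, …) ≤ proportion with at least one event ≤ min(100%, r1 + r2 + …).

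Illustration with assumed rates of 10%, 15% and 15%:

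- Lower bound (full overlap): max = 15%; 0.15 × 290 = 43.5, about 44 subjects.
- Upper bound (no overlap): 10 + 15 + 15 = 40%; 0.40 × 290 = 116 subjects.

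Other assumed sets of five rows, with the same formula:

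| Assumed PT rates (%) | Largest row | Sum of rows |
|---|---|---|
| 5, 5, 4, 3, 2 | 5% | 19% |
| 15, 12, 10, 8, 5 | 15% | 50% |
| 25, 20, 20, 15, 10 | 25% | 90% |

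The N of 290 is from Protocol 1.5.1; every rate is an assumption. The general result does not depend on the rates: unless the rows overlap completely or not at all, the table leaves the composite undetermined.

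**The case against.** **Every event is reported somewhere.** This is correct, and it limits the point. SAP 15.1.1 tabulates all TEAEs, and separately those judged related, by SOC and PT with no time window or term restriction. The PT Acute Phase Reaction counts after any infusion. A reader might infer that the incidence of the reaction is never stated, or that its symptoms are undercounted throughout the report. The documents support neither: what is missing is the composite, and any undercount is confined to the reaction table and listing. The subject listing would also allow a hand count of the composite, but on the same list without diarrhea and not as a planned output.

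**The first-infusion window is an error.** A reader might infer this because symptoms that are only decreased later are not absent, and because an episode after a later infusion counts if coded Acute Phase Reaction but not if coded Pyrexia and Myalgia. The unevenness is real, but the window follows the protocol. Protocol 1.4.3, 6.3 and 8.2 all tie these symptoms chiefly to the first administration. Three-day windows after infusions on Days 1, 4, 7 and 10 (±1 day, at least 48 hours apart) would abut or overlap. They would also take in more Pain and Pain In Extremity events in subjects enrolled for limb pain. This is a trade-off, not a defect.

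**Ocular events belong in the composite.** Protocol 8.2 says: "Eye disorders have been reported with neridronic acid and appear to be associated with the acute phase reaction". That is cautious wording under a separate heading, and the symptom list contains no ocular term. Ocular inflammation also has its own pre-infusion assessment and its own entries in Table 2 of Protocol 9.3.2. Merging it with flu-like symptoms could obscure a distinct risk.

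**Nothing confirmatory depends on this.** This is true. All analyses are exploratory, and the primary and secondary safety endpoints are unaffected. The point concerns how well one prominent safety finding is described.

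**Conclusion.** The point holds in limited form. The acute phase reaction list in SAP 15.1.1 omits one of the eight symptoms named in Protocol 8.2, and its table cannot give the proportion of subjects with at least one event. Both follow from the text and need no assumption about rates.

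The size cannot be stated from the documents. The range of 15% to 40% only illustrates how loosely PT rows bound the composite under assumed rates. A reader might also try to count subjects lost because they react first to a later infusion. If 30% react to infusion 1 and 2% to 5% of the rest react first later, that is 290 × 0.70 × 0.02 = 4.1 to 290 × 0.70 × 0.05 = 10.2 subjects. Those rates have no source in the documents, and the loss is zero if nobody reacts first to a later infusion. It should not be cited as an expected undercount.

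No event goes uncollected or untabulated. The change is worth making because it is cheap and fixes the composite before the final analysis.

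**What to change.** In SAP 15.1.1:

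- Add the PT Diarrhoea to the symptom list, under the same first-infusion window and other conditions as the existing 12 PTs.
- Add a first row to the acute phase reaction table with the number and percentage of Safety Set subjects with at least one event meeting the definition.

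The cost is SAP wording and one reprogrammed table and listing, using adverse event and infusion dates and times already collected. The downside is that a few unrelated diarrhea events will be counted, so the figure becomes slightly less favourable.

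Two additions are optional. One is a separate supportive display of the same PTs with onset after infusions 2 to 4, assigning each event to the most recent infusion so that overlapping windows cause no ambiguity. The other is a separate row for the ocular events described in Protocol 8.2, kept out of the composite.
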